 Mount Sinai	Protocol Name:	A double-blinded, placebo-controlled study to evaluate the tolerability and efficacy of Enstilar® (calcipotriene and betamethasone dipropionate) Foam in the treatment of chronic plaque psoriasis in patients with skin of color (Fitzpatrick skin phototypes IV-VI).
	Principal Investigator:	[name], MPH
	Primary Contact Name/Contact Info:	[name], MPH [contact]
	Date Revised:	08/10/2017
	Study Number:	IF2166478

3. Ongoing use of other psoriasis treatment including but not limited to topical or systemic corticosteroids, other topical medications (i.e. coal tar), oral or biologic medications for the treatment of psoriasis, and UV therapy. The following washout periods will be required:
 - 2 weeks for topical therapy
 - 2 weeks for phototherapy
 - 12 weeks for biologic or targeted therapies
 - 4 weeks for other systemic therapies
4. Use of oral estrogen therapy, excluding oral contraceptive pills
5. Women who are pregnant, nursing, or of child-bearing potential who are unwilling to use appropriate method(s) of contraception.
6. Patients unwilling to limit exposure to UV light
7. Current significant medical problems that, in the discretion of the investigator, would put the patient at significant risk
8. Patients with disorders of calcium metabolism and/or hypercalcemia.
9. Use of any investigational drug within 4 weeks prior to randomization, or 5 pharmacokinetic/pharmacodynamics half-lives, if known (whichever is longer).
10. History of allergy to any component of the IP

c) Number of Subjects

Patients with skin types IV-VI with chronic plaque-type psoriasis will be screened with a goal of 25 total subjects randomized. All 25 randomized subjects are expected to complete all study procedures. Individuals who provide informed consent and fail to meet all of the inclusion and exclusion criteria during the initial evaluation will be considered a “screening failure.”

d) Study Timelines

The study will consist of 6 visits over up to 12 weeks (up to 4 week screening period plus 8 weeks enrolled in study). Study visits will be conducted at Screening (Visit 1), Baseline (Visit 2, Week 0), Week 1 (Visit 3), Week 2 (Visit 4), Week 4 (Visit 5), and Week 8/discontinuation (Visit 6).

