 Mount Sinai	Protocol Name:	A double-blinded, placebo-controlled study to evaluate the tolerability and efficacy of Enstilar® (calcipotriene and betamethasone dipropionate) Foam in the treatment of chronic plaque psoriasis in patients with skin of color (Fitzpatrick skin phototypes IV-VI).
	Principal Investigator:	[name], MPH
	Primary Contact Name/Contact Info:	[name], MPH [contact]
	Date Revised:	08/10/2017
	Study Number:	IF2166478

Enrollment will occur over a 6 month period from November 2017 to May 2018.

e) Endpoints

Primary Endpoint:

1. Investigator Global Assessment (IGA mod 2011) at week 4

Proportion of patients at week 4 who achieved treatment success according to investigator global assessment (IGA mod 2011) of the entire body including scalp. IGA will range from 0 (clear) to 4 (severe). Treatment success is defined as IGA of clear (0) or almost clear (1) for patients with \geq moderate disease at baseline or IGA of clear (0) for patients with mild disease at baseline.

Secondary Endpoints:

1. Psoriasis Area and Severity Index 50 and 75 (PASI50 and PASI75) at weeks 2, 4, and 8.

Proportion of patients achieving $\geq 50\%$ improvement and/or $\geq 75\%$ improvement in Psoriasis Area and Severity Index (PASI) at weeks 4 and 8 compared to baseline (PASI 50 and PASI 75, respectively). PASI will be completed by the investigator or trained qualified designee at screening and weeks 0, 2, 4, and 8.

2. Psoriasis Scalp Severity Index 50 and 75 (PSSI50 and PSSI75) at weeks 2, 4 and 8, if applicable

Proportion of patients achieving $\geq 50\%$ improvement and/or $\geq 75\%$ improvement in Psoriasis Scalp Severity Index (PSSI) at weeks 4 and 8 compared to baseline (PSSI 50 and PSSI 75, respectively), if applicable. PSSI will be completed by the investigator or trained qualified designee at screening and weeks 0, 2, 4, and 8 if the subject has/had scalp involvement at the baseline visit.

3. Investigator Global Assessment (IGA mod 2011) at weeks 2 and 8

Proportion of patients at week 8 who achieved treatment success according to investigator global assessment (IGA mod 2011) of the entire body including scalp. IGA will range from 0 (clear) to 4 (severe). Treatment success is defined as IGA of clear (0) or almost clear (1) for patients with \geq moderate disease at baseline or IGA of clear (0) for patients with mild disease at baseline.

4. Scalp Investigator Global Assessment (ScIGA) at weeks 4 and 8, if applicable

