9. Change in physician dyspigmentation visual analog scale (VAS) at weeks 4 and 8.

An investigator will perform a visual analog scale (VAS) rating the degree of dyspigmentation of the skin. This VAS will range from - 5 to 5 as follows: 5 severe dark

 Mount Sinai	Protocol Name:	A double-blinded, placebo-controlled study to evaluate the tolerability and efficacy of Enstilar® (calcipotriene and betamethasone dipropionate) Foam in the treatment of chronic plaque psoriasis in patients with skin of color (Fitzpatrick skin phototypes IV-VI).
	Principal Investigator:	[name], MPH
	Primary Contact Name/Contact Info:	[name], MPH [contact]
	Date Revised:	08/10/2017
	Study Number:	IF2166478

brown pigmentation (darkest imaginable color), 4 dark brown pigmentation, 3 medium brown pigmentation, 2 light brown pigmentation, 1 slight dark pigmentation (barely perceptible compared to surrounding skin), 0 baseline skin pigmentation, -1 slight hypopigmentation (barely perceptible compared to surrounding skin), -2 mild hypopigmentation (light brown), -3 moderate hypopigmentation (creme-colored skin), -4 severe hypopigmentation (almost complete absence of pigment), -5 depigmentation (complete absence of pigment). This VAS will be performed at baseline and weeks 4 and 8.

10. Change from baseline in Dermatology Life Quality Index (DLQI) total score at weeks 2, 4 and 8.

Subjects will complete a DLQI at baseline, week 2, week 4 and week 8. Change in DLQI total score between baseline and week 4 will be assessed.

 Mount Sinai	Protocol Name:	A double-blinded, placebo-controlled study to evaluate the tolerability and efficacy of Enstilar® (calcipotriene and betamethasone dipropionate) Foam in the treatment of chronic plaque psoriasis in patients with skin of color (Fitzpatrick skin phototypes IV-VI).
	Principal Investigator:	[name], MPH
	Primary Contact Name/Contact Info:	[name], MPH [contact]
	Date Revised:	08/10/2017
	Study Number:	IF2166478

a) Procedures Involved in the Human Research

Table 1: Assessment Schedule

	Visit	1	2	3	4	5	6
	Week	-4 to BL	0 (BL)	1	2	4	8 ET/E OT
	Visit Window (days)			±2	±2	±5	±5
Assessment							
Informed Consent		X					
Demographics		X					
Inclusion/Exclusion		X	X				
Medical History		X					
Psoriasis treatment history		X					
AE/SAE assessment		X	X	X	X	X	X
Concomitant medications		X	X	X	X	X	X
Vital Signs		X					
Height and Weight		X					
Physical Examination		X					
Fitzpatrick Skin Type assessment		X					
Photography			X			X	X

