Urine Pregnancy Test		X	X				
BSA		X	X		X	X	X
Investigator IGA mod 2011 score (and ScIGA if applicable)		X	X		X	X	X
PASI score (PSSI if applicable)		X	X		X	X	X
Mexameter measurement of erythema and melanin indices			X		X	X	X
Investigator dyspigmentation VAS			X			X	X
Patient Global Assessment of severity (PaGA)			X		X	X	X
Patient pruritus VAS			X	X	X	X	X
Patient dyspigmentation VAS			X			X	X
Dermatology Life Quality Index (DLQI)			X		X	X	X
Local Tolerability Assessment			X	X	X	X	X
Treatment satisfaction evaluation					X	X	X
Study Drug Training			X				
Study Drug Dispensation and Return			X			X	X

 Mount Sinai	Protocol Name:	A double-blinded, placebo-controlled study to evaluate the tolerability and efficacy of Enstilar® (calcipotriene and betamethasone dipropionate) Foam in the treatment of chronic plaque psoriasis in patients with skin of color (Fitzpatrick skin phototypes IV-VI).
	Principal Investigator:	[name], MPH
	Primary Contact Name/Contact Info:	[name], MPH [contact]
	Date Revised:	08/10/2017
	Study Number:	IF2166478

This is a single-center study and will consist of 3 phases. Phase 1 - screening phase, Phase 2 - Double-blinded, vehicle-controlled phase, and Phase 3 - Open-label and maintenance phase

Phase 1 - The screening phase will last up to 28 days. Screening and baseline may occur on the same day if subject does not require a wash-out period.

Phase 2 - double-blinded, placebo-controlled phase to evaluate the tolerability and efficacy of Enstilar® (calcipotriene and betamethasone dipropionate) Foam versus placebo in the treatment of chronic plaque psoriasis in patients with skin of color (Fitzpatrick skin phototypes IV-VI). This phase will last 4 weeks (baseline to week 4). Subjects will be randomized in a 4:1 ratio to Enstilar® or placebo, respectively. The study product will be applied once daily for 4 weeks.

Phase 3 - Open-label and maintenance phase. Subjects who were randomized to placebo during phase 2 will receive Enstilar daily x 4 weeks. Subjects who were randomized to Enstilar during phase 2 will switch to Enstilar twice weekly x 4 weeks as maintenance treatment.

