Prior to the start of the study, potential subjects will be given an IRB-approved Informed Consent Document (ICD) containing a Health Insurance Portability and Accountability Act (HIPAA) disclosure agreement to read, understand, and sign. After providing informed consent, subjects will be assessed for study eligibility at the Screening visit. The PI or a medically qualified designee must review this information (i.e. medical history, concomitant medication, and eligibility review) for each subject to confirm their eligibility before enrollment.

A total of 25 subjects who meet eligibility criteria will undergo Baseline / Day 0 assessments. At this Baseline visit, subjects will undergo randomization to either active drug or vehicle. All subjects will receive study drug training. Study drug will be dispensed at baseline and week 4. Un-used drug will be returned to the site at each visit.

Subjects will return for visits at weeks 1, 2, 4, and 8 so that a review of concomitant medications and adverse events can be assessed. The PI or designee will interview the subjects to collect and record any adverse events (AEs) or changes to health/concomitant medications that may have occurred since the previous visit. Additional procedures and assessments will be performed as outlined in table 1.

If a subject terminates early or chooses to discontinue the study, he/she will be asked to return for a final visit, at which time the procedures for visit 6 will be performed.

Enstilar® foam is a combination of calcipotriene 0.005%, a vitamin D analog, and betamethasone dipropionate 0.064%, a corticosteroid. Enstilar® foam is indicated the treatment of plaque psoriasis in patients 18 years of age and older.

 Mount Sinai	Protocol Name:	A double-blinded, placebo-controlled study to evaluate the tolerability and efficacy of Enstilar® (calcipotriene and betamethasone dipropionate) Foam in the treatment of chronic plaque psoriasis in patients with skin of color (Fitzpatrick skin phototypes IV-VI).
	Principal Investigator:	[name], MPH
	Primary Contact Name/Contact Info:	[name], MPH [contact]
	Date Revised:	08/10/2017
	Study Number:	IF2166478

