6. N/A
7. Adverse events will be graded using the Common Terminology Criteria for Adverse Events (CTCAE).
8. The study will be conducted in compliance with regulatory requirements and Good Clinical Practice. Quality control will be applied to each stage of data handling to ensure that data are accurate, reliable and processed correctly.
9. Should a temporary or permanent suspension of our study occur, the occurrence will be reported to the PPHS, sponsor, and IRB.

Part II. Data Monitoring Committee/Data Safety Monitoring Board (DMC/DSMB)

N/A

e) Withdrawal of Subjects

When an individual who has signed the ICF is not enrolled in the study or withdraws/is withdrawn prior to completing the study, the reason is to be documented on the Discontinuation/Completion Form (or equivalent) and in the final study report. Reasons for subject withdrawal may include:

 Mount Sinai	Protocol Name:	A double-blinded, placebo-controlled study to evaluate the tolerability and efficacy of Enstilar® (calcipotriene and betamethasone dipropionate) Foam in the treatment of chronic plaque psoriasis in patients with skin of color (Fitzpatrick skin phototypes IV-VI).
	Principal Investigator:	[name], MPH
	Primary Contact Name/Contact Info:	[name], MPH [contact]
	Date Revised:	08/10/2017
	Study Number:	IF2166478

- Not enrolled (e.g. fails to meet inclusion/exclusion criteria, chooses not to enroll, etc.)
- Participant is determined to be ineligible after enrollment
- Subject's choice to withdraw
- Investigator terminated (e.g. noncompliance, etc.)
- Adverse Event
- Lost to follow-up
- Other

Subjects may withdraw from the trial at any time at their request, or they may be withdrawn at any time at the discretion of the Sponsor, PI, or designee for safety, behavioral, or administrative reasons. Subjects may be withdrawn from this study without their consent if the research study is being stopped; or if the instructions of the study team have not been followed.

If a subject does not return for a scheduled visit, *three documented attempts will be made to contact the subject in order to establish the reason for withdrawal, and the outcome will be documented.* The PI or designee should inquire about the reason for withdrawal, request that the subject return for a final visit, if applicable, and follow-up with the subject regarding any unresolved adverse events.

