Should a subject withdraw from the trial and also withdraw consent for disclosure of future information, no further evaluations should be performed and no additional data should be collected. The PI and staff may retain and continue to use any data collected before such withdrawal of consent. Removed or withdrawn subjects will not be replaced.

If a subject fails to report to the test facility for a scheduled visit and cannot be rescheduled within the permitted window of time (as applicable), the Site should consult with the Sponsor to determine if the subject should be documented as having withdrawn/dropped from the study.

2) Risks to Subjects

The following list of side effects is the ones that may be associated with the use of Enstilar® foam:

Observed in less than 1% of subjects (based on clinical trials):

- Application site reactions:
 - Irritation
 - Pruritus
- Folliculitis
- Skin hypopigmentation

 Mount Sinai	Protocol Name:	A double-blinded, placebo-controlled study to evaluate the tolerability and efficacy of Enstilar® (calcipotriene and betamethasone dipropionate) Foam in the treatment of chronic plaque psoriasis in patients with skin of color (Fitzpatrick skin phototypes IV-VI).
	Principal Investigator:	[name], MPH
	Primary Contact Name/Contact Info:	[name], MPH [contact]
	Date Revised:	08/10/2017
	Study Number:	IF2166478

- Hypercalcemia
- Urticaria
- Exacerbation of psoriasis

Observed uncommon adverse reactions (based on post-marketing data):

- Atrophy of thin skin
- Telangiectasia of the skin
- Dryness of the skin
- Perioral dermatitis
- Secondary infections of the skin
- Miliaria

Other warnings:

- **Hypercalcemia and hypercalciuria** – Hypercalcemia and hypercalciuria have been observed with the use of Enstilar® foam. If either of these conditions develop, Enstilar® should be discontinued until calcium levels normalize in the blood and/or urine.
- **Endocrine system effects** – The systemic absorption of topical corticosteroids may lead to reversible suppression of the hypothalamic-pituitary-adrenal (HPA) axis, which may result in clinical glucocorticoid insufficiency either during treatment or upon withdrawal of the topical steroid. The risk of HPA axis suppression is higher with use of high-potency steroids, treatment of a large surface area, prolonged use, use of occlusive dressings, altered skin barrier, liver failure, and young age.

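### Any early stop leads to one exit visit that shares the Week 8 slot, so a subject who stops before about day 23 can lack the Week 4 IGA that is the primary endpoint

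*Protocol*

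**What the plan says.** **Exit rule.** Under a) Procedures Involved in the Human Research, a subject who terminates early or discontinues is handled by one rule: "he/she will be asked to return for a final visit, at which time the procedures for visit 6 will be performed". The rule does not depend on when the subject stops, and it sets no day for the exit visit.

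**Visit label.** Section 5) d) Study Timelines names the last slot "Week 8/discontinuation (Visit 6". Table 1 does the same, with one column for Week 8 and early termination or end of treatment.

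**Who leaves.** Section e) Withdrawal of Subjects lists "Investigator terminated (e.g. noncompliance, etc" among the reasons, beside adverse event, subject's choice and loss to follow-up. It adds: "Removed or withdrawn subjects will not be replaced".

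**Primary endpoint.** Section e) Endpoints defines it as "Proportion of patients at week 4 who achieved treatment success according to investigator global assessment (IGA mod 2011", that is, at Visit 5, the end of the double-blind phase. After it, vehicle subjects change to Enstilar and Enstilar subjects change to the maintenance schedule.

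**Completion.** Section c) Number of Subjects expects all 25 randomised subjects to complete every procedure.

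**The concern.** The protocol provides one route for a subject who stops early: a single exit visit, then out. It mentions reactions that require the product to be stopped (Local Tolerability Assessment) but gives no visit schedule for a subject who stops product and is willing to be seen again.

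A subject who stops in the first three weeks can therefore have an exit IGA but no IGA at Week 4. An analysis plan can decide how to treat the gap. It cannot supply an observation that nobody asked for. In a vehicle arm of five, one such gap is a large part of the comparison.

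The shared label is a smaller matter. An exit reading taken on blinded product is recorded in the same slot as readings taken after the Week 4 change of treatment, and the visit number alone will not tell the two apart.

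**Working it through.** **Inputs from the protocol**
- 25 randomised at 4:1 (synopsis and Phase 2 description).
- Baseline is Day 0 (Procedures).
- The Table 1 row "Visit Window (days" gives ±2 days at Weeks 1 and 2, and ±5 days at Weeks 4 and 8.
- The Table 1 row "Investigator IGA mod 2011 score (and ScIGA if applicable" is marked at Visits 1, 2, 4, 5 and 6, so not at Week 1.

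**1. Arm sizes.** 25 × 4/5 = 20 Enstilar and 25 × 1/5 = 5 vehicle. This reproduces the protocol's 20 and 5.

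**2. Where an exit visit falls**
- Week 4: 28 ± 5 = days 23 to 33.
- Week 8: 56 ± 5 = days 51 to 61.
- An exit visit on days 23 to 27 is inside the Week 4 window and includes an IGA, so a usable Week 4 reading exists.
- An exit visit before day 23 is outside both windows. The subject then has an exit IGA, and perhaps a Week 2 IGA, but none at Week 4.
- What counts is the date of the exit visit, which the protocol does not fix. That is why the Week 4 reading can be missing rather than must be.

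**3. Weight of one missing reading**
- Vehicle: 1/5 = 20 percentage points. If r of the other four succeed, the rate for all five lies between r/5 and (r + 1)/5. With r = 0 that is 0% to 20%.
- Enstilar: 1/20 = 5 percentage points.

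Any rule for missing data picks a value in that range. Only an assessment closes it.

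**4. How likely it is.** The protocol gives no dropout rate beyond full completion. Let d be the assumed proportion with no Week 4 reading, independent between subjects. Expected number = 25d. Chance of at least one in the vehicle arm = 1 − (1 − d)^5.

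| Assumed d | Expected among 25 | At least one of 5 vehicle |
|---|---|---|
| 4% | 1.0 | 1 − 0.96^5 = 18.5% |
| 10% | 2.5 | 1 − 0.90^5 = 41.0% |
| 20% | 5.0 | 1 − 0.80^5 = 67.2% |

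**5. Cost of asking for Week 4.** The Visit 5 and Visit 6 columns of Table 1 mark the same assessments. Visit 5 is already scheduled for everyone, so nothing new has to be designed.

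**The case against.** The strongest reply is that the exit rule says which assessments to perform, not the time point under which they are analysed. Analysis windows and missing-data rules usually sit in the SAP, which is not shown. IGA is taken at exit, so something is collected. A subject who has truly left has no Week 4 value whatever the visit is called, and relabelling creates none. Staff must also make three contact attempts after a missed visit and, where applicable, request a final visit.

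Most of this stands, and it rules out three stronger readings that a reader might infer.

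- *That the protocol puts double-blind readings into the Week 8 endpoints.* It does not say so. The endpoints are defined by week, and an exit before Week 4 cannot meet the days 51 to 61 window. It would happen only if data were analysed by visit number without regard to dates.
- *That early leavers are dropped from the primary denominator.* No section states an exclusion.
- *That the trial loses a calculable amount of power.* The protocol states no test, significance level or response rates. A power figure would need all of these, plus an assumed exclusion rule and an assumed split of losses between arms.

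The reply does not cover the subject who stops product or is judged noncompliant but has not withdrawn consent. The protocol bars further evaluation only where consent for future information is also withdrawn. The others could be seen at Week 4, and the text does not ask them. That is a data-collection gap, which an SAP cannot repair afterwards.

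**Conclusion.** The point holds as a gap in data collection. Following the protocol as written can lose the primary reading of a subject whose exit visit falls before day 23, when many such subjects could be assessed at an already scheduled visit. One lost vehicle reading leaves 20 percentage points of that arm undetermined; one lost Enstilar reading leaves 5.

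How often this happens is unknown. The 18.5% to 67.2% range rests on assumed loss of 4% to 20%, and if all 25 complete, as the protocol expects, it does not arise. The figures also treat every early stop as avoidably unassessed. Subjects who withdraw consent or cannot be reached would still be missing, so attendance at Week 4 would recover some readings, not all.

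The shared Visit 6 label is a recording ambiguity, worth correcting at the same time but not an error in any endpoint. The change is a cheap improvement that should be made; the design does not fail without it.

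**What to change.** 1. **Separate the two events.** In the early-termination paragraph under Procedures and in e) Withdrawal of Subjects, distinguish stopping study product from withdrawing from the study.
2. **Ask for Week 4.** State that a subject who stops product or is noncompliant before Week 4, and who has not withdrawn consent for further assessment, is asked to attend the scheduled Week 4 visit (days 23 to 33) for IGA and the other Visit 5 assessments. Keep the single exit visit for those who leave the study.
3. **Label the exit visit.** Give early termination its own visit label in Study Timelines, Table 1 and the CRF, with the actual date recorded, so that an exit reading from the double-blind period is not stored as Week 8.

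This changes no rule on when product is stopped. Analysis windows and the treatment of a Week 4 IGA that is still missing belong in the SAP.

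Cost: a few lines of protocol text, one CRF label and a little more retention effort. Some Week 4 readings will be taken off product, and the SAP will need to say how they are used. No visit or procedure is added to the schedule.

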Chronic plaque psoriasis classically presents as sharply demarcated erythematous plaques with micaceous scale. Nonetheless, there are notable differences in psoriasis presentation in skin of color groups. Black patients with psoriasis tend to have less erythema, increased risk of pigmentation, thicker plaques, more scaling, and greater body involvement as compared to white patients.^{5,6,7} Several studies suggest that erythema is more challenging to detect in skin of color, and inflammation that typically manifests as pink or red lesions in lighter skin may appear violaceous or hyperpigmented in darker skin types.⁸ The resolution of psoriasis lesions in darker skin types is associated with a higher rate of dyspigmentation (both hyper- and hypo-pigmentation), which may be more bothersome to patients than the psoriasis itself.^{7,8}

Further, several studies have shown that psoriasis is associated with greater psychological impact and worse QOL in non-whites with psoriasis compared to whites.^{5,8,9,10} Dermatology Life Quality Index (DLQI) scores are consistently lower in blacks and Hispanics compared to whites, even when controlling for body surface area affected and severity of disease.¹⁰

Despite differences in psoriasis between whites and non-whites, there is paucity of data on the use of topical medications in dark-skinned individuals.^{11,12} Unique issues in SOC populations, including masking of erythema and high risk of post-inflammatory pigmentary sequelae, make studies dedicated to darker skin types essential for treatment of psoriasis in these populations.

Combination of calcipotriene and betamethasone dipropionate 0.005%/0.064% aerosol foam (Enstilar®) has been shown to be effective in the treatment of mild or greater plaque psoriasis when used once daily for 4 weeks.^{13,14,15} Use of Enstilar® has also been associated with significant improvement in health-related quality of life.¹⁶ Nonetheless, pivotal phase II and III trials of Enstilar® included a predominately white population; 87.1% of subjects in three pooled US phase II and III pivotal trials were white.¹⁷ Given the small number of non-white subjects, it is difficult to make meaningful comparisons between different race/ethnicity subgroups.¹⁷

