Medical History and Concomitant Medications: At the screening visit, subjects will be asked about current medical conditions or history of any medical conditions. Subjects will also be asked about current medication use and use of medications for 1 month prior to screening. Concomitant medications will be reviewed and recorded at every scheduled visit.

Psoriasis Treatment History: At the screening visit, subjects will be asked about their current and all past treatments for psoriasis, including over-the-counter and prescription therapies.

Vital Signs: Vital signs will be assessed at the screening visit. Whether action needs to be taken regarding abnormal vital signs (as defined below) will be at the investigator's discretion. After the

 Mount Sinai	Protocol Name:	A double-blinded, placebo-controlled study to evaluate the tolerability and efficacy of Enstilar® (calcipotriene and betamethasone dipropionate) Foam in the treatment of chronic plaque psoriasis in patients with skin of color (Fitzpatrick skin phototypes IV-VI).
	Principal Investigator:	[name], MPH
	Primary Contact Name/Contact Info:	[name], MPH [contact]
	Date Revised:	08/10/2017
	Study Number:	IF2166478

subject has been sitting for at least five minutes with back supported and both feet on the ground, systolic and diastolic blood pressure (BP) will be measured using an appropriately sized cuff. Pulse will also be measured using either an automated machine or manually. Normal Blood pressure will be defined as systolic 90 to <120mmHg and diastolic 60 to <80mm Hg. Notable blood pressure will be hypertension (systolic \geq 140 mmHg and/or diastolic \geq 100 mmHg). A normal pulse rate will be defined as 60 to 100 beats per minute. Notable pulse rates will be defined as bradycardia (<50bpm) and tachycardia (>100bpm).

Height and Weight: Height and weight will be measured by a designated site individual at the screening visit.

Physical examination: Physical examination will be performed by the investigator, sub-investigator, or other qualified individuals at screening. This will include examination of the heart, lungs, abdomen, extremities, and skin, as well as any additional body systems as deemed necessary by the investigator.

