Dermatology Life Quality Index (DLQI): DLQI is a validated 10-question questionnaire developed to address quality of life in patients with dermatological disorders. It has previously been used with success to assess the impact of psoriasis on quality of life. Patients will be asked to fill out a DLQI at baseline, week 2, week 4, and week 8.

Patient Satisfaction Questionnaire: Subjects will be asked to complete a questionnaire asking about satisfaction with the study product, including satisfaction with the product vehicle, ease of application, and overall satisfaction with the treatment product.

Local Tolerability Assessment: Assessment of local safety and tolerability will be completed at baseline and weeks 1, 2, 4, and 8. The investigator or designated site staff will assess for: perilesional erythema, edema, dryness, and erosion. These parameters will be graded on a scale of 0 (absent) to 3 (severe). The subjects will also be asked about application site burning and pain after application of the study drug. Subjects will be asked to grade their burning/stinging from 0 (absent) to 3 (severe). Only severe site reactions or reactions that require discontinuation of the study product will be recorded as AEs.

 Mount Sinai	Protocol Name:	A double-blinded, placebo-controlled study to evaluate the tolerability and efficacy of Enstilar® (calcipotriene and betamethasone dipropionate) Foam in the treatment of chronic plaque psoriasis in patients with skin of color (Fitzpatrick skin phototypes IV-VI).
	Principal Investigator:	[name], MPH
	Primary Contact Name/Contact Info:	[name], MPH [contact]
	Date Revised:	08/10/2017
	Study Number:	IF2166478

Urine Pregnancy test: Urine pregnancy test will be performed at screening and baseline visits for women of child-bearing potential. A woman is considered post-menopausal if she has not had a menstrual period in >12 months.

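### Four skin reactions that the protocol names as risks are not graded on the tolerability form, and mild or moderate cases may be neither graded nor recorded as adverse events

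*Protocol*

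**What the plan says.** All places are in the Protocol.

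- **Local Tolerability Assessment, investigator items.** "The investigator or designated site staff will assess for: perilesional erythema, edema, dryness, and erosion". Each is scored 0 to 3.
- **Local Tolerability Assessment, subject items.** "The subjects will also be asked about application site burning and pain after application of the study drug". Burning or stinging is also graded 0 to 3.
- **Timing.** "Assessment of local safety and tolerability will be completed at baseline and weeks 1, 2, 4, and 8".
- **Recording rule in the same paragraph.** A site reaction becomes an adverse event only if it is severe or leads to discontinuation of the product.
- **Adverse Events and Serious Adverse Events.** Every adverse event is to be recorded by the investigators from consent to the end of follow-up. A pre-existing condition counts only if it worsens.
- **Risks to Subjects.** Folliculitis is listed among reactions seen in under 1% of trial subjects. The uncommon post-marketing reactions include "Atrophy of thin skin", telangiectasia and perioral dermatitis.
- **Physical examination.** "Physical examination will be performed by the investigator, sub-investigator, or other qualified individuals at screening". It covers the skin, but no grade is specified and Table 1 does not repeat it.
- **Photography.** Whole-body front and back views are taken at baseline and Weeks 4 and 8.

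**The concern.** Tolerability is in the title and safety is in the objective. The reader of the final report will look to the tolerability table for local skin safety, yet that table cannot contain four of the reactions that the protocol itself tells subjects to expect as possible.

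The filter on site reactions makes this worse. For the graded signs the filter does little harm, because a mild or moderate case still leaves a score on the form. For a reaction that is not on the form, the same filter can remove the only remaining record. A later analysis plan cannot recover a sign that was never graded or written down.

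The baseline matters too. Subjects may have used topical corticosteroids until two weeks before entry, and worsening of a pre-existing condition is hard to judge without a starting grade.

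**Working it through.** **1. Named risks against routes of capture**

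| Named skin reaction | Graded on tolerability form | Other dedicated scale |
|---|---|---|
| Dryness | yes | – |
| Pruritus | no | subject pruritus VAS |
| Hypopigmentation | no | dyspigmentation VAS, melanin index |
| Psoriasis exacerbation | no | IGA, PASI, BSA |
| Folliculitis | no | none |
| Atrophy | no | none |
| Telangiectasia | no | none |
| Perioral dermatitis | no | none |

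The last four appear among neither the four investigator signs nor the subject items. Secondary infection and miliaria, also named, have no graded item either. With 25 subjects and 5 tolerability visits there are 25 × 5 = 125 scheduled assessments, 25 of them at baseline, and none carries a grade for these reactions. That count describes the form; it is not an effect size.

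**2. The two recording rules side by side**

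The tolerability paragraph admits only severe or discontinuing site reactions to the adverse event record. The adverse event section admits everything, without exception. The term site reaction is not defined in the tolerability paragraph, so there are two readings for a mild folliculitis or early atrophy that the investigator sees:

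- *It is a site reaction.* It is not on the form, and the filter keeps it out of the adverse event record. No entry results.
- *It is not a site reaction.* The general rule applies and it should be recorded, with no grade on the form and no graded baseline.

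The Risks to Subjects list appears to place irritation and pruritus under application site reactions and folliculitis as a separate entry. That leans towards the second reading for folliculitis, but the tolerability paragraph does not refer to that list.

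**3. How many cases might there be?**

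The plan gives no figure to reproduce. Inputs: 20 subjects on active and 5 on vehicle in the blinded phase, with all 25 due to receive active by Week 8. The rate for folliculitis is stated only as under 1%; no rates are given for the other three, so a range is assumed.

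P(at least one case) = 1 − (1 − p)^n

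| Rate p | n = 20 | n = 25 |
|---|---|---|
| 0.1% (assumed) | 2.0% | 2.5% |
| 0.5% (assumed) | 9.5% | 11.8% |
| 1% (ceiling for folliculitis) | 1 − 0.99^20 = 18.2% | 1 − 0.99^25 = 22.2% |
| 5% (assumed) | 64.2% | 72.3% |

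With zero cases observed, the one-sided 95% upper bound is 1 − 0.05^(1/n): 13.9% for n = 20 and 11.3% for n = 25.

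**The case against.** The strongest case on the other side is that these reactions are not left unexamined. Table 1 schedules adverse event assessment at all six visits, and the adverse event section makes the investigators responsible for recording. Qualified site staff score IGA, PASI and BSA at Weeks 2, 4 and 8, and the PASI regions include face, axillae and groin. The screening examination includes the skin, photographs give a visual baseline, and one exclusion criterion bars other active skin disease that could interfere with lesion assessment. Cases will probably be few, and even a graded zero in 25 could not show absence.

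Most of this stands. A reader might infer that the reactions would not be looked for, that there is no baseline at all, or that existing atrophy could never be told from new. The documents do not support those readings, given the routes just listed. Nor do they say how well subjects notice or report such changes.

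The objection does not close the gap in the record. IGA, PASI and BSA score the psoriasis and have no field for these signs. No passage at hand assigns the photographs to safety reading. Seeing a mild reaction does not help if the recording rule may tell the investigator not to enter it. That conflict is in the text and does not depend on how many cases occur.

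The opening items of the Data and Safety Monitoring Plan are not in the copy at hand and could contain further adverse event provisions.

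**Conclusion.** The point holds in a limited form. The four named reactions are not graded and have no graded baseline, and mild or moderate cases may be neither graded nor recorded as adverse events. The second part rests on reading them as site reactions under an undefined term, and on there being no further recording rule in the part of the monitoring plan that could not be read.

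The consequence is an incomplete safety description in a trial that sets out to assess tolerability. The primary endpoint and its analysis are unaffected. If folliculitis occurs at up to 1%, there is at most about a one-in-five chance (22.2%) of any case in 25 subjects; for the other three the rate is unknown. Better recording would give descriptive data only. It would let the report say that the signs were systematically graded, which it cannot say now.

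**What to change.** 1. In the Local Tolerability Assessment, add investigator-graded items on the existing 0 to 3 scale for skin atrophy, telangiectasia, and folliculitis or perioral eruption, at baseline and Weeks 1, 2, 4 and 8. Have the assessor note which eruption is meant in the combined item.
2. Report these items as shift from the baseline grade.
3. Reconcile the recording rule in the Local Tolerability Assessment with the one in the adverse event section, and define site reaction, so that a non-severe reaction that is not graded on the form still leaves a record. This also covers secondary infection and miliaria, which the added items do not.

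The cost is three more lines on an existing form, with the same assessor, scale and visits. Assessments become slightly longer, most noticeably at Week 1, where Table 1 schedules no other investigator skin scoring. The change concerns measurement and recording only.
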